### **Parameters with NCI-CTC grades not available:**

Hematology and chemistry evaluations which cannot be graded per CTCAE criteria will be summarized as frequency (number and percentage) of patients with:

- shifts from baseline normal to at least one result above normal during on-treatment period
- shifts from baseline normal to at least one result below normal during on-treatment period

In this study, these apply to the following parameters:

- Hematology: Absolute Monocytes, Absolute Eosinophils, Absolute Basophils
- Serum Chemistry: Chloride, Total Urea, Uric Acid, Total Protein, C-Reactive Protein, Lactate Dehydrogenase (LDH)

### **6.6.5.2. Other laboratory parameters**

The listings of laboratory results will be provided for all laboratory parameters. The listings will be sorted by parameters and assessment dates or visits for each patient. Laboratory values that are outside the normal range will also be flagged in the data listings, along with corresponding normal ranges.

### **6.6.6. Vital signs**

Weight for the purposes of dose calculation will be recorded at screening and within 3 days pre-dose Day 1 of each cycle. Height will be measured at screening only.

### **6.6.7. Electrocardiogram**

ECG summaries will include all ECG assessments from the on-treatment period. QTcB and QTcF will be derived based on RR and QT (see below). The average of the replicate measurements should be determined after the derivation of the individual parameter at each time point.

### **Selecting Primary QT Correction for Heart Rate**

The analysis of QT data is complicated by the fact that the QT interval is highly correlated with heart rate. Because of this correlation, formulas are routinely used to obtain a corrected value, denoted QTc, which is independent of heart rate. This QTc interval is intended to represent the QT interval at a standardized heart rate. Several correction formulas have been proposed in the literature. For this analysis we will use some of those methods of correction, as described below. The QT interval corrected for heart rate by the Bazett's formula, QTcB, is defined as

$$QTcB = \frac{QT}{\sqrt{RR}}$$

the QT interval corrected for heart rate by the Fridericia's formula, QTcF, is defined as

$$QTcF = \frac{QT}{\sqrt[3]{RR}}$$

where RR represents the RR interval of the ECG, in seconds, and can be estimated as 60/Heart Rate.

Although Bazett's correction is the historical standard, it does not perform well when heart rate fluctuates. Fridericia's formula may perform better under these conditions. Data will be summarized using QTcF and QTcB.

### **ECG Summaries**

The following analyses will be performed for each applicable ECG parameters (RR, PR, QRS, QT, ventricular rate -denoted as HR in what follows-, and QTc) by treatment group, during the on-treatment period. The denominator to calculate percentages for each category is the number of patients evaluable for the category.

- Pearson correlation between QT and HR, QTc (QTcB and QTcF) and HR using individual (non-averaged) baseline assessments
- Frequency (number and percentage) of patients with notable ECG values according to the following categories:
  - QT/QTc increase from baseline >30 ms, >60 ms
  - QT/QTc > 450 ms, > 480 ms, > 500 ms
  - HR ≤ 50 bpm and decrease from baseline ≥ 20 bpm
  - HR ≥ 120 bpm and increase from baseline ≥ 20 bpm
  - PR ≥ 220 ms and increase from baseline ≥ 20 ms
  - QRS ≥ 120 ms

Unscheduled ECG measurements will not be used in computing the descriptive statistics for change from baseline at each post-baseline time point. However, they will be used in the analysis of notable ECG changes and the shift table analysis of notable QT parameters.

## **7. INTERIM ANALYSES**

There is no formal interim analysis planned for this study.

## 9. APPENDICES

### Appendix 1. Immune-Related Adverse Events

The MedDRA PTs and clusters for irAEs are defined in the Safety Review Plan (SRP) for avelumab.

Immune-related AEs (irAEs) will be programmatically identified as outlined in Table 15. This case definition is hierarchical, ie, each step is only checked for patients and events that have already met the prior step.

**Table 15. Case Definition for irAEs**

Step	Selection Criteria	Additional Notes
1	Event selected based on a list of pre-specified MedDRA PTs within clusters. These are included in the SRP as Tier1 events (Immune-mediated xxxx). If AE matches the list, then it is in for the next step	
2	AE onset during 1 st study drug administration or anytime thereafter through 90 days after last dose of study treatment.	This is regardless of start of new anti-cancer drug therapy and regardless of TEAE classifications
3	Answer in the AE eCRF page to ‘Was another treatment given because of the occurrence of the event’ is ‘YES’	Steps 3 and 4 will be checked concurrently. Step 5 will be checked if the criteria in Step 4 is met, irrespective of whether the Criteria in Step 3 is met.
4	AE treated with corticosteroids or other immunosuppressant therapy. For endocrinopathies only: AE required hormone replacement	Look in the conmed pages for AE identifiers that match the AEs from Step 3. For each of such AEs if A) OR B) OR C) below are met then the AE is in for the next step A) conmed ATC code is in (H02A, H02B, D07, A01AC, S01BA, S01BB, L04AA, L04AB, L04AC, L04AD, L04AX, A07EA) and AE PT is in any of the irAE clusters. B) conmed ATC code is in (H03A, H03B) and AE PT is in one of the irAE clusters associated with “Immune-mediated endocrinopathies” C) conmed ATC code is A10A and AE PT is in the irAE cluster associated with “Immune-mediated endocrinopathies: Type I Diabetes Mellitus”

5	
A) No clear etiology (other than immune mediated etiology)
 
B) Histopathology / biopsy consistent with immune-mediated event
 
Event is in if          [Answer to 5B1 and 5B2 is YES (regardless of answer to 5A)]          OR          [Answer to 5B1 is YES AND answer to 5B2 is NO AND answer to 5A is NO]          OR          [Answer to 5B1 is NO AND answer to 5A is NO]
	
A) From the AE eCRF page.          Is the AE clearly related to an etiology other than immune-mediated etiology? Yes / No          If answer is Yes, check all that apply:
 
 
• Underlying malignancy / progressive disease.
 
• Other medical conditions.
 
• Prior or concomitant medications / procedures.
 
• Other. Specify.
 
 
B) From the AE eCRF page.          B1) Was there a pathology /histology evaluation performed to investigate the AE? Y/N          B2) If answer to the above is Yes, does the pathology/histology evaluation confirms an immune mediated mechanism for the AE? Y/N          B3) If pathology / histology evaluation performed to investigate the AE, provide summary of relevant findings of the pathology /histology report. (Free Text)

---	---	--

The data set associated with irAEs may be refined based on medical review. The final data set including any changes based on medical review (eg, addition of cases that are not selected by the programmatic algorithm) will be the basis of the irAE analyses.

## Appendix 2. Infusion Related Reactions

For defining an AE as IRR, the onset of the event in relation to the infusion of study drug and time to resolution of the event will be considered.

- All AEs identified by the MedDRA PT query describing signs and symptoms will be considered potential IRRs when onset is on the day of study drug infusion (during or after infusion) and the event resolved with end date within 2 days after onset.
- All AEs identified by the MedDRA PTs of Infusion related reaction, Drug hypersensitivity, Anaphylactic reaction, Hypersensitivity, Type 1 hypersensitivity, will be considered potential IRRs when onset is on the day of study drug infusion (during or after the infusion) or the day after the study drug infusion (irrespective of resolution date).

The list of MedDRA PTs for ‘IRRs SIGNS and SYMPTOMS’ and PTs ‘IRRs CORE’ are defined in the SRP for avelumab.

Infusion-related reactions (IRRs) will be programmatically identified as outlined in Table 16 or Table 17 and will be identified for IV drugs only.

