**Important for Combination F:** CMP-001 activates pDCs through agonism of TLR9. Upon activation by CMP-001, pDCs will induce large amounts of IFN $\alpha$  and Th1-promoting cytokines. Therefore, it is expected that toxicities associated with CMP-001 dosing may resemble interferon-related toxicities and symptoms associated with cytokine release, such as fever, flu-like symptoms, tachypnea, headache, tachycardia, hypotension, rash, and hypoxia which may present hours after CMP-001 injection. Therefore, AEs such as headache, fever, flu-like symptoms and/or hypotension that are  $\leq$  Grade 3 AND resolved to  $\leq$  Grade 1 within 24 hours with standard supportive care will not be considered as DLTs.

- Non-hematologic Grade  $\geq 3$  laboratory abnormality if medical intervention is required to treat the patient or the abnormality leads to hospitalization.
  - Single laboratory values out of normal range that are unlikely related to trial treatment according to the Investigator, do not have any clinical correlate, and resolve to Grade  $\leq 1$  within 7 days with adequate medical management are not to be considered DLTs;
  - ALT or AST  $> 3$  x upper limit of normal (ULN) (if normal at baseline) or  $> 3$  x ULN and doubling the baseline (if  $> ULN$  at baseline) associated with bilirubin  $> 2$  x ULN.

Non-Adherence to Treatment Schedule:

- Delay of  $\geq 3$  weeks in receiving the next scheduled administration due to persisting treatment-related toxicities;
- Failure to receive at least 75% of the planned doses each of the investigational products during the DLT observation period due to treatment-related toxicities.

In the absence of associated clinical abnormalities, abnormal laboratory tests should be repeated to confirm relevance.

While the rules for adjudicating DLTs in the context of the dose determination phase (Phase 1b) are specified above, an AE not listed above, or an AE meeting the DLT criteria above but occurring outside of the DLT observation period may be defined as a DLT after consultation between Sponsor and Investigator, based on the emerging safety profile.

- Phase 2: Confirmed objective response (OR), as assessed by the Investigator using RECIST v1.1.

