### **6.6.4. Other significant adverse events**

The frequency (number and percentage) of patients with each of the following will be presented for irAEs, by treatment group:

- irAEs, by Cluster, PT, and maximum CTCAE Grade
- irAEs leading to discontinuation of avelumab, by Cluster and PT
- irAEs leading to discontinuation of any study drug by Cluster and PT
- Serious irAEs, by Cluster and PT

The listing of all irAEs will also be provided with the relevant information with a flag for irAEs with onset outside of the on-treatment period.

The frequency (number and percentage) of patients with each of the following will be presented for IRRs, by treatment group and for each study drug:

- IRRs, by PT and maximum CTCAE grade
- IRRs leading to discontinuation of avelumab, by PT
- IRRs leading to discontinuation of any study drug, by PT
- Serious IRRs, by PT
- Time related to first onset of an IRR (infusion 1, infusion 2, infusion 3, infusion 4 or later). For IV study drugs administered in combination the infusion numbers are those associated with the regimen, rather than the individual study drugs.

The listing of all IRRs will also be provided with the relevant information with a flag for IRRs with onset outside of the on-treatment period.

For Combination F only (Cohorts F1, F2 and F3) Cytokine Release Syndrome (as defined in the SRP) may be summarized and listed as described above for irAEs by Cluster and PT or by PT only, as applicable.

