**Table 16. Case Definition for IRRs – IV Study Drugs Administered Alone Or In Combination With Non-IV Study Drugs**

Condition	Selection criterion
If AE meets [1 AND 2] OR [3 AND (4A OR 4B)] then AE is classified as an IRR	
1	PT is included in the ‘IRRs SIGNS and SYMPTOMS’ list
2	
 
• AE onset date = date of infusion of study drug AND
 
• AE timing related to study drug (‘DURING’, ‘AFTER’) AND
 
• AE outcome in (‘RECOVERED/RESOLVED’, ‘RECOVERED/RESOLVED WITH SEQUELAE’, ‘RECOVERING/RESOLVING’) AND
 
• AE end date – AE onset date <math>\leq 2</math>
 

3	PT is included in the ‘IRRs CORE’ list
4A	
 
• AE onset date = date of infusion of study drug AND
 
• AE timing related to study drug in (‘DURING’, ‘AFTER’)
 

4B	AE onset on the day after infusion

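### In Combination F, a listed short-lived symptom after an IV infusion is classified as an infusion reaction of the IV drug(s) even when CMP-001 was given that day

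*SAP*

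**What the plan says.** The SAP builds the IRR set by program in Appendix 2. For symptom terms the first test is on timing: such events "will be considered potential IRRs when onset is on the day of study drug infusion (during or after infusion"). A duration test is then added: "and the event resolved with end date within 2 days after onset". The preferred-term lists "are defined in the SRP for avelumab", the Safety Review Plan (SRP), which the SAP does not reproduce. IRRs "will be identified for IV drugs only".

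Table 16 is headed "IV Study Drugs Administered Alone Or In Combination With Non-IV Study Drugs", so it governs Cohort F1, where avelumab is the only IV drug. Its rule is deterministic: "If AE meets [1 AND 2] OR [3 AND (4A OR 4B)] then AE is classified as an IRR". Table 17 applies where several IV drugs are given, as in F2 and F3, and lets one AE be associated with more than one of them.

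Section 6.6.4 then states that patient frequencies "will be presented for IRRs, by treatment group and for each study drug".

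For Combination F, Section 3.1 says that CMP-001 toxicity may include fever along with "flu-like symptoms, tachypnea, headache, tachycardia, hypotension, rash, and hypoxia which may present hours after CMP-001 injection". Some of these AEs are exempted from being DLTs if they fall to Grade 1 or lower within 24 hours.

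**The concern.** The reactions that Section 3.1 expects from CMP-001 can have the features that the IRR rule looks for: a systemic symptom, starting some hours after dosing, and over quickly. When CMP-001 and an IV antibody are given on the same day, the rule cannot tell the two causes apart. CMP-001 is not an IV drug, so it can never be the drug charged. The event goes to the antibody by default.

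What is at stake is the per-drug IRR table for F1 to F3. Reactions to the newly added non-IV agent could appear there as infusion reactions to avelumab, utomilumab or PF-04518600, and nothing in the planned table would warn the reader. A smaller downstream effect is that Section 6.6.1.2 removes IRRs that only interrupted an infusion from the analysis of AEs leading to interruption, so an event misclassified in this way could drop out there too. The DLT assessment and the response analysis do not use the IRR flag and are not affected.

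**Working it through.** **1. What the rule tests.** Table 16, conditions 1 and 2, requires all of the following: preferred term on the signs-and-symptoms list; onset date equal to the infusion date; timing during or after the infusion; outcome resolved, resolved with sequelae, or resolving; end date minus onset date of at most 2 days. Conditions 2A1 and 2A2 of Table 17 make the same tests for each IV drug in turn. None of them tests causality, same-day CMP-001 dosing or membership of a CRS event.

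**2. The rule applied to a listed, recovered symptom with onset on the infusion day:**

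| Timing v infusion | Duration 0, 1 or 2 days | Duration 3 days |
|---|---|---|
| Before | not an IRR | not an IRR |
| During | IRR | not an IRR |
| After | IRR | not an IRR |

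The table is the same whether the true cause is avelumab or CMP-001. In F2 or F3, a symptom that starts after both IV infusions meets 2A2 and is charged to both drugs.

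**3. CMP-001 calendar, checked against the SAP's own figure.** Section 3.4.1 gives 7 weekly doses of 10 mg (2 SC, then 5 IT), followed by Q2W dosing. Counting from Day 1 in 28-day cycles:
- Cycle 1: Days 1, 8, 15, 22, so 4 × 10 = 40 mg
- Cycle 2: Days 29, 36, 43, so 3 × 10 = 30 mg
- Cycle 3: Days 57, 71, so 2 × 10 = 20 mg
- Cycle 4: Days 85, 99, so 2 × 10 = 20 mg

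This reproduces the intended 40, 30 and 20 mg per cycle in Section 6.5.3.5.

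**4. Overlap with avelumab.** Avelumab is given Q2W: nominal Days 1, 15, 29, 43, 57, 71 and so on. The SAP gives frequencies but does not say that the two drugs share a start day, so the offset is an assumption and is varied here.
- Offset 0 (both start on Day 1): the shared days among the first 7 CMP-001 doses are 1, 15, 29 and 43, so 4 of 7. Every later Q2W dose (57, 71, 85, ...) is also shared.
- Offset 1 day: no shared days. Four of the first 7 doses (Days 2, 16, 30, 44) fall on the day after an infusion, where only terms on the core list count (condition 4B).
- Offsets 2 to 6 days: none of the doses falls on an infusion day or on the day after one.

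**5. The reverse count at offset 0.** Avelumab Days 1, 15, 29, 43, 57, 71, ... are all CMP-001 days while CMP-001 continues. Nominally, no infusion day is then free of CMP-001. This limits what a split by dosing date can show.

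**6. Safeguards.** Appendix 1 allows medical review to refine the irAE set. Appendix 2 has no such step for IRRs. Section 6.6.1.1 has a CRS line for Combination F, and Section 6.6.4 says further CRS summaries may be produced. Neither says how an event that meets both definitions is handled.

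**The case against.** The strongest reply is that the definition is openly temporal. Appendix 2 speaks of potential IRRs, Table 17 lets one AE attach to several drugs, and the heading of Table 16 shows that non-IV partners were foreseen. An over-inclusive rule may have been chosen on purpose. That explains the rule, but not why its output is tabulated for each study drug without a caveat.

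Several stronger readings are tempting, and the document does not support them.
- *Every short-lived symptom on the day is charged to the IV drugs.* It is not. The term must be on the list, and the timing, outcome and duration conditions must all be met. Reactions on CMP-001-only days fall outside the rule.
- *The SAP says that CMP-001 reactions end within 2 days.* It does not. The 24-hour wording is a DLT exemption and concerns return to Grade 1 or lower, not an AE end date. A fever that lingers at Grade 1 to a third day after onset would fail the duration test. A reaction starting hours later may also begin on the next calendar date.
- *The CMP-001 safety signal is hidden.* It is not. Section 6.6.1.1 still gives all TEAEs and related TEAEs by preferred term and worst grade, discontinuations of CMP-001 and the CRS line.
- *Counting one event under both IRR and CRS is an error.* The categories in Section 6.6.1.1 overlap by design. What is missing is a statement that these two may overlap.

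Section 6.6.1 also says that the term list is finalized for this study before database lock. Changing the list cannot separate two causes of the same symptom.

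**Conclusion.** The concern stands as a defect in per-drug reporting for Combination F. On a day when CMP-001 and an IV drug are both given, an AE that meets the listed conditions is classified as an IRR of the IV drug(s) whatever its cause, and the SAP itself expects look-alike reactions from CMP-001.

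The size cannot be computed. It depends on two things the SAP does not give: which terms the SRP list holds, and whether dosing days coincide. For the signs-and-symptoms rule the range runs from nil (no shared days) to exposure of 4 of the first 7 CMP-001 doses and all later Q2W doses (common Day 1 start, nominal schedule). These are dosing occasions at risk, not events. A reader might want to turn them into a number of patients or an inflated avelumab IRR rate, but that would need a CMP-001 reaction rate, and the SAP has none.

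**What to change.** Change Appendix 2 and Section 6.6.4, for F1 to F3 only. This alters reporting and touches no dose or clinical rule.

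1. Flag each programmatic IRR whose onset date is a CMP-001 dosing date, or which is part of an event classified as CRS.
2. Report flagged and unflagged IRRs separately by treatment group. Do not present flagged events as attributable to an individual IV drug. Footnote that they are temporal and may be CMP-001 reactions.
3. Where the investigator's relationship is recorded by study drug, show flagged IRRs by that relationship.
4. Extend the medical-review step of Appendix 1 to IRRs.
5. State that an event may appear in both the IRR and the CRS lines.

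The unflagged row should not be read as avelumab's IRR rate. If dosing days coincide, few IRRs will be unflagged, and a true IV reaction on a shared day will sit among the flagged events. Showing both rows keeps it visible.

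The cost is SAP wording, one flag derived from CMP-001 dosing dates and the CRS classification, and a few extra rows.

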#### **5.3.2.2. Adverse events**

Incomplete AE-related dates will be imputed as follows:

- If the AE onset date is missing completely, then the onset date will be replaced by the start of study treatment.
- If only the day part of the AE onset date is missing, but the month and year are equal to the start of study treatment, then the AE onset date will be replaced by the start of study treatment. For example, if the AE onset date is --/JAN/2015, and study treatment start date is 15/JAN/2015, then the imputed AE onset date will be 15/JAN/2015.
- If both the day and month of the AE onset date are missing but the onset year is equal to the start of study treatment, then the onset date will be replaced by the start of study treatment. For example, if AE onset date is --/--/2014, and study treatment start date is 19/NOV/2014, then the imputed AE onset date will be 19/NOV/2014.
- In all other cases the missing onset day or missing onset month will be replaced by 1.
- Incomplete stop date will be replaced by the last day of the month (if day is missing only), if not resulting in a date later than the date of patient's death. In the latter case the date of death will be used to impute the incomplete stop date.
- In all other cases the incomplete stop date will not be imputed. If stop date of AE is after the date of cut-off outcome of AE is ongoing at cut-off.

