#### **6.6.1.2. Adverse events leading to interruption of study treatment**

The eCRF does not allow for a clear separation between interruption of an infusion and delays of administration for a parenteral drug as both are recorded using the same term on the eCRF (“Drug interrupted”). IRRs will be excluded in the analysis of AEs leading to Drug Interruption in case they only led to an interruption of the infusion (ie, did not lead to a dose reduction or a dose delay).

As such, AEs leading to interruption will be defined as AEs identified in the AE eCRF page with an action taken with study treatment of ‘drug interrupted’ excluding

- IRRs that occurred on the day of infusion with  $\geq 90\%$  of the planned dose given (ie IRRs that did not lead to a dose reduction) and subsequent administration of study drug had no delay (as defined in Section 6.5.3.6). These IRRs will be considered as IRRs leading to interruption of infusion.
- IRRs occurring on the day after infusion and subsequent dose administration had no delay (as defined in Section 6.5.3.6).

The frequency (number and percentage) of patients with each of the following will be presented for TEAEs leading to interruption of each study drug by treatment group:

- TEAEs leading to interruption of avelumab by SOC and PT
- TEAEs leading to interruption of utomilumab by SOC and PT
- TEAEs leading to interruption of PF-04518600 by SOC and PT
- TEAEs leading to interruption of PD 0360324 by SOC and PT

The listing of all AEs leading to interruption of study treatment will also be provided with the relevant information.

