2A2	
 
• AE onset date = date of infusion of study drug DJ AND
 
• AE timing related to study drug DJ (‘DURING’, ‘AFTER’) AND
 
• AE timing related to study drug DJ+1 (‘DURING’, ‘AFTER’) AND
 
• AE outcome in (‘RECOVERED/RESOLVED’, ‘RECOVERED/RESOLVED WITH SEQUELAE’, ‘RECOVERING/RESOLVING’) AND
 
• AE end date – AE onset date ≤ 2
 

3	PT is included in the ‘IRRs CORE’ list
4A1	
 
• AE onset date = date of infusion of study drug DJ AND
 
• AE timing related to study drug DJ (‘DURING’, ‘AFTER’) AND
 
• [AE timing related to study drug DJ+1 (‘BEFORE’) OR AE onset date < date of infusion of study drug DJ+1]
 

4A2	
 
• AE onset date = date of infusion of study drug DJ AND
 
• AE timing related to study drug DJ (‘DURING’, ‘AFTER’) AND
 
• AE timing related to study drug DJ+1 (‘DURING’, ‘AFTER’)
 

4B	AE onset on the day after infusion of study drug D J

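### Month-end imputation of a day-missing AE stop date makes truly short infusion-day symptoms fail the 2-day IRR test; few events may be affected, but Appendix 2 should state its own rule

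*SAP*

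**What the plan says.** Section 5.3.2.2 opens with a general scope: "Incomplete AE-related dates will be imputed as follows". For stop dates the rule is "Incomplete stop date will be replaced by the last day of the month (if day is missing only". If the month end would fall after the patient's death, "In the latter case the date of death will be used to impute the incomplete stop date". For anything less complete, "In all other cases the incomplete stop date will not be imputed".

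Appendix 2 identifies IRRs by program, for IV drugs only, through Table 16 or Table 17. Its text asks of a signs-and-symptoms term that "the event resolved with end date within 2 days after onset". In the tables, such a term must satisfy "AE onset date = date of infusion of study drug", have timing recorded as during or after the infusion, have a recovered or recovering outcome, and meet "AE end date – AE onset date ≤ 2". The duration line stands in Table 16 condition 2 and in Table 17 conditions 2A1 and 2A2. Core terms (infusion related reaction, hypersensitivity, anaphylactic reaction and the like) qualify whatever their resolution date.

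Section 6.6.1.2 links the IRR label to a second table: "IRRs will be excluded in the analysis of AEs leading to Drug Interruption in case they only led to an interruption of the infusion". For an infusion-day IRR this also requires that at least 90% of the planned dose was given and that the next dose was not delayed.

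**The concern.** Month-end imputation takes the longest duration compatible with the recorded month. That is cautious when a long event is the worry. The IRR test requires a short event, so the same convention works against detection.

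Take chills on an infusion day of 5 January, outcome recovered, stop date recorded only as January. The imputed stop date is 31 January, the difference is 26 days, and the event is not an IRR even if it ended within the hour.

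IRRs are adverse events of special interest (Section 3.5.1), so a loss of this kind lowers a table that readers will look at. An affected event with action taken 'drug interrupted' also stays in the interruption table, if it would otherwise have met all the exclusion conditions of Section 6.6.1.2. Appendix 1 lets medical review add irAE cases that the algorithm missed; Appendix 2 states no such step for IRRs.

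**Working it through.** The SAP gives no figure on this point, so there is none to reproduce. The check is a calendar count.

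**Inputs**
- From Section 5.3.2.2: stop date = last day of the recorded month when only the day is missing.
- From Tables 16 and 17: the event passes if end date minus onset date is at most 2.
- Assumptions: onset date complete and on the infusion day; infusion days spread evenly over the calendar; no death before the month end; 2016 to 2019 used as an illustrative calendar (1,461 days, 48 months).

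**Events that truly resolved the same day.** With a month-end stop date, the event passes only if onset falls on one of the last 3 days of the month. In a month of L days the share failing is (L − 3)/L:
- L = 28: 25/28 = 89.3%
- L = 29: 26/29 = 89.7%
- L = 30: 27/30 = 90.0%
- L = 31: 28/31 = 90.3%

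Over the four years, 48 × 3 = 144 onset days pass. The share failing is 1 − 144/1,461 = 90.1%. With weekday infusions only it is 90.0%.

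**Events that truly lasted 1 or 2 days.** An event that crosses into the next month is imputed to the end of that next month and fails.
- 1 day: 2 onset days per month pass, 48 × 2 = 96; failing 1 − 96/1,461 = 93.4%.
- 2 days: 1 onset day per month passes, 48; failing 1 − 48/1,461 = 96.7%.

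**Events that truly lasted more than 2 days.** All fail, which is correct. The imputation creates no false IRRs, so the error runs in one direction.

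**Effect on all truly short symptom reactions.** Let m be the share of them whose stop date lacks only the day. The SAP does not give m. The share lost is between 0.901 × m and 0.967 × m:
- m = 0: nothing lost
- m = 1%: 0.9% to 1.0%
- m = 2%: 1.8% to 1.9%
- m = 5%: 4.5% to 4.8%
- m = 10%: 9.0% to 9.7%

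**Patient scale (illustration).** Suppose 10 patients in a cohort each have one symptom IRR. Then m = 1% loses about 10 × 0.009 = 0.09 patients and m = 10% loses up to 10 × 0.097 = 0.97. A patient with a second reaction under the same term and a complete stop date is still counted.

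**Earliest-date alternative.** Set the stop date to max(onset date, first day of the stop month). No event of 0 to 2 days is then lost, but longer events with such dates can pass:
- 3 days: 1 − 48/1,461 = 96.7% pass
- 5 days: 1 − 144/1,461 = 90.1% pass
- 10 days: 1 − 384/1,461 = 73.7% pass (8 onset days per month fail, 48 × 8 = 384)

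**The case against.** The strongest reply is that this is an edge case. The affected event must be a signs-and-symptoms term with a complete infusion-day onset date, an accepted outcome and a stop date lacking only the day. Section 2 says the analysis uses cleaned eCRF data, and an event timed as during or after an infusion is not an obvious source of partial stop dates. The tables count patients once per term, and infusions are repeated. No event disappears: it stays in the TEAE, related and serious tables and loses only its IRR label. Requiring documented resolution within 2 days for non-specific symptoms is also a defensible case definition. All of this stands, and it limits the size.

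A reader might infer that about 90% of infusion reactions are lost, or that they are lost whatever their true duration. The SAP supports neither. The 90% is a share of same-day events with a partial stop date, longer events should fail, and core terms are untouched. Nor does every affected event with action 'drug interrupted' move into the interruption table; the dose and no-delay conditions of Section 6.6.1.2 must also hold.

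It is also fair that any fixed rule misclassifies some events: the earliest-date rule admits longer ones. That bears on how the remedy is reported. It does not remove the defect, because a programmer who follows the SAP as written will let an imputed date decide a 2-day criterion, and no stated step recovers the event.

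**Conclusion.** The point holds in a limited form. For signs-and-symptoms terms, Section 5.3.2.2 feeds a month-end stop date into the 2-day test of Appendix 2. Among events with a day-missing stop date, 90.1% of those that resolved the same day, 93.4% of 1-day events and 96.7% of 2-day events are wrongly left out of the IRR set. These shares rest on infusion days being spread evenly over the calendar and on complete onset dates; death before the month end is a minor exception.

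The effect on the IRR tables depends on how many such dates exist. The SAP does not say, and it may be close to none, so the effect is probably small. The effect on the interruption table is narrower still. This is worth settling before database lock because the direction is against detecting an event of special interest and the correction costs little.

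**What to change.** Add to Appendix 2, for the IRR derivation only:
- Where an AE stop date lacks only the day and the outcome is one that Tables 16 and 17 accept (including recovering/resolving), set the stop date to max(onset date, first day of the stop month).
- Flag these events in the IRR listing, and report the IRR count with and without them.
- Leave events with a wholly missing stop date unclassified by the 2-day rule, but list them. Treating them as meeting the rule would remove the resolution criterion.

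Leave Section 5.3.2.2 unchanged for all other uses.

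The cost is a sentence or two of text, a few lines of code and one extra count. The downside is that some events longer than 2 days with a partial stop date will be counted as IRRs (about 97% of 3-day and 74% of 10-day events with such dates). The flag and the two counts let a reader see how much this matters.
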